Neratinib (Nerlynx®), an orally available, irreversible tyrosine kinase inhibitor (TKI), was approved by the Food and Drug Administration (FDA) in 2017 and in the European Union (EU) in 2018. In the EU, Neratinib's approved indication is for extended adjuvant therapy of adult patients with early-stage Hormone Receptor-positive (HR+) HER2-overexpressed/amplified breast cancer and who completed prior adjuvant trastuzumab-based therapy less than one year ago. The recommended dose of neratinib is 240 mg (six 40 mg tablets) taken orally once daily, continuously for one year¹⁵. Comparatively, the FDA approved indication applies to a broader profile of patients, where neratinib as a single agent is approved for the extended adjuvant

 Pierre Fabre TEMP CQA 0092 V2.0 Owning site : CORPORATE QA	Template to use for writing Corporate document, except Corporate policy and form, WORD in english	Page 10/29
--	--	------------

therapy of adult patients with early-stage HER2-positive breast cancer, to follow adjuvant trastuzumab-based therapy. Nothing is specified in terms of HR status or the length of prior adjuvant trastuzumab-based therapy.

Certain patients may have received neratinib as per the FDA indication, as part of the EAP in Europe.

Results of the ExteNET trial showed that patients with early-stage HER2+ breast cancer receiving one year of extended adjuvant therapy with oral neratinib (within a year of standard of care adjuvant trastuzumab), had significant improvement in the 2-year iDFS rate compared to placebo (93.9% versus 91.3%, respectively; hazard ratio, 0.67; 95% Confidence Interval (CI), 0.50–0.91; $p = 0.0017$)¹⁶. A 5-year follow-up reported similar results (hazard ratio 0.73; 95% CI 0.57–0.92; $p=0.008$)¹⁷. Furthermore, greater improvement in iDFS was observed in HER2+ patients with HR+ breast cancer¹⁶⁻¹⁸.

An Early access program (EAP) was initiated in Europe in 2017, providing access to neratinib to individual patients following specific criteria outside of a clinical trial. This program is currently ongoing in certain European countries, awaiting product reimbursement. This study will provide real-world data to characterize the profile of patients treated with neratinib, their previous medical history, the conditions for using neratinib and its profile in terms of safety and effectiveness as an extended adjuvant therapy. The profile of patients may be more diverse compared to those enrolled in the ExteNET trial.

Rationale

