8.4 Examination of Subgroups

The following subgroups are of interest, based on patient characteristics at neratinib initiation (index date) or primary diagnosis of breast cancer. Analyses of primary, secondary, and exploratory outcomes may be performed for some or all these subgroups, subject to pertinence and the number of patients in each subgroup:

- EU label status: Yes, No
 - Yes, defined as, HR+ patients with initiation of Neratinib ≤ 1 year from trastuzumab-based treatment completion in adjuvant setting (EU Label population)
 - No, otherwise
- Pathologic stage (AJCC classification) at primary breast cancer: Stage I, Stage II+III
 - If missing, derived as in 2
- Residual disease after neoadjuvant treatment (pathologic complete response [pCR]): pCR, No pCR

- Risk: Low risk (Stage I or N- or pCR), High risk (Stage II/III or N+ or no pCR)
 - N-, defined as, the electronic case report form (eCRF) nodal status category of NX or N0
 - N+, defined as $N \geq 1$ nodal
- Previous adjuvant or neoadjuvant therapy ⁽²⁾: Neoadjuvant + Post neoadjuvant treatment, Adjuvant only
 - Neoadjuvant + Post neoadjuvant, defined as, at least one neoadjuvant and one adjuvant treatment
 - Adjuvant only, defined as, at least one adjuvant treatment and no neoadjuvant
- Prior trastuzumab-based regimen overall (neoadjuvant or adjuvant): Trastuzumab only, Trastuzumab and Pertuzumab, Trastuzumab emtansine (T-DM1), Other anti HER2
- Prior trastuzumab based regimen the last treatment in adjuvant setting before Neratinib initiation: Trastuzumab only, Trastuzumab and Pertuzumab, Trastuzumab emtansine (T-DM1), Other anti HER2
- Hormone Receptor at Primary Breast Cancer Diagnosis: HR+, HR-
 - HR+, defined as either ER or PR or both are positive
 - HR-, defined as if ER and PR are negative
- Concomitant Corrective Antidiarrheal: Yes, No
- Concomitant Prophylaxis Antidiarrheal: Yes, No
- Initial Dose of Neratinib: <240mg, 240mg, >240mg

Table 2 AJCC staging

Primary tumor (T)	Regional lymph nodes (N)	Distant metastasis (M)	Stage
Tis	N0	M0	0
T1	N0	M0	IA
T0	N1	M0	IB
T1	N1	M0	IB
T0	N1	M0	IIA
T1	N1	M0	IIA
T2	N0	M0	IIA
T2	N1	M0	IIB
T3	N0	M0	IIB
T0	N2	M0	IIIA
T1	N2	M0	IIIA
T2	N2	M0	IIIA
T3	N1	M0	IIIA
T3	N2	M0	IIIA
T4	N0	M0	IIIB
T4	N1	M0	IIIB
T4	N2	M0	IIIB
Any T	N3	M0	IIIC
Any T	Any N	M1	IV

N2 and N3 are not collected in the CRF, this regional lymph node categories will be identified by “ ≥ 4 ” lymph nodes involved.

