12.3.1 Neoadjuvant and Adjuvant Therapy

The following variables will be presented as frequencies and percentages and summary statistics as appropriate, for neoadjuvant therapy (pre-surgery) and adjuvant therapy (post-surgery), separately, for FAS and by subgroup EU label; Pathological stage; Risk profile (section 8.4). For adjuvant therapy analysis will also be performed by subgroup Previous adjuvant or neoadjuvant therapy (section 8.4).

- Number and percentage of patients with at least one therapy. Percentage computed among FAS.
- Number of therapies by patient
- Number and percentage of patients by therapy combinations of any therapy type. Percentage computed among FAS.
- Number and percentage of patients by therapy combination category: Chemotherapy (+/- Endocrine therapy), Chemotherapy + Trastuzumab (+/- Endocrine therapy), Chemotherapy + Trastuzumab + Pertuzumab (+/- Endocrine Therapy), TDM1 (+/- Endocrine therapy) (for adjuvant only) and Other (+/- Endocrine therapy).
- Duration of treatment (months)⁽¹⁾, calculated as:
 - (*End date - Start date + 1*) / 30.4
- Outcome: pCR, No pCR (for the neoadjuvant therapy overall)

- Number and percentage of patients by neoadjuvant/adjuvant therapies received. Percentage computed among FAS.
- For each therapy type (Chemotherapy, Endocrine Therapy, Anti-HER2, Immunotherapy, Other):
 - Number and percentage of patients by therapy name. Percentage computed among FAS with each treatment type.
 - Number and percentage of patients by therapy combination. Percentage computed among FAS with each treatment type.
 - Duration of treatment (months)⁽¹⁾, defined as:
 - $(End\ date - Start\ date + 1) / 30.4$
 - Number and percentages of patients who stopped the treatment as initially planned: Yes, No
 - If no, the reason: Toxicity, Worsening condition, No response/ Partial response, Physician's decision, Patient's wish, Other
 - Outcome: pCR, No pCR (in neoadjuvant therapy only)

⁽¹⁾A patient can contribute with multiple therapies, the duration of treatment will correspond to the total exposure of the patient to the treatment type.

Additionally, for anti-HER2, the therapy combinations will also be presented.

In the adjuvant setting, for anti-HER2, the number and percentage of patients by Prior trastuzumab-based regimen (last treatment) will be presented.

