Appendix 1. Partial Date Conventions

No imputation of missing data will be performed; missing data will not be replaced in this study, unless specified and for the following dates (Table 8). Imputed dates will not be presented in the listings.

Table 8 Missing data imputation rules

Variable	Rule
General rule for partial dates	If the day of event is missing and month and year are available: the day will be imputed to the first day of the month, in case of a start date, and to the last day of the month, in case of an end date. Unless such imputation is illogical. If the day and month are missing, the date will not be imputed.
Date of abstraction	Will not be imputed
Date of informed consent/ non-opposition	Will not be imputed
Date of primary diagnosis of Breast Cancer	General rule for partial dates applies.
Date of pregnancy	Will not be imputed
Start date (Pre-/Post-surgery neoadjuvant therapy)	Will not be imputed.
End date (Pre-/Post-surgery neoadjuvant therapy)	Will not be imputed.
Date of surgery	Will not be imputed.
Date of radiotherapy	Will not be imputed.
Date of weight measurement	General rule for partial dates applies.
Date of performance status assessment (follow-up)	Will not be imputed.
Neratinib initiation date	General rule for partial dates applies.

Variable	Rule
Neratinib definitive discontinuation Date	General rule for partial dates applies.
Treatment modification date	Will not be imputed.
Treatment temporary discontinuation date	Will not be imputed.
Treatment date of re-initiation	Will not be imputed.
Concomitant treatment start date	General rule for partial dates applies.
Concomitant treatment end date	General rule for partial dates applies.
Start date of AE	General rule for partial dates applies.
Date of death	General rule for partial dates applies.
Admission date (Hospitalization due to AE)	Will not be imputed.
Discharge date (Hospitalization due to AE)	Will not be imputed.
Date of recurrence (AE recurrence)	Will not be imputed.
Date of recovery (AE outcome)	Will not be imputed.
Date of first breast cancer recurrence	General rule for partial dates applies.
Treatment start date (Breast cancer recurrence)	General rule for partial dates applies.
Treatment end date (Breast cancer recurrence)	General rule for partial dates applies.
Date of last contact	General rule for partial dates applies.
Date of consent withdrawn	Will not be imputed.

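### EU label status has no level for patients who cannot be classified, so an undeterminable trastuzumab interval or receptor status is counted as off-label

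*SAP*

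**What the plan says.** SAP 8.4 gives EU label status two levels. Yes is "Yes, defined as, HR+ patients with initiation of Neratinib ≤ 1 year from trastuzumab-based treatment completion in adjuvant setting (EU Label population"); No is the remainder. The split was added in the SAP (section 7.10) and does not appear among the protocol's subgroups.

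Two neighbouring definitions in 8.4 are more careful. HR-negative status needs positive evidence: "HR-, defined as if ER and PR are negative". Pathologic stage has a rule for gaps: "If missing, derived as in 2". EU label status has neither safeguard.

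SAP Appendix 1, Table 8, has a row "End date (Pre-/Post-surgery neoadjuvant therapy"), marked as not to be imputed. SAP 12.3.1 describes treatment history "for neoadjuvant therapy (pre-surgery) and adjuvant therapy (post-surgery), separately", which equates post-surgery with adjuvant. The default for dates that Table 8 does not list is also no imputation: "No imputation of missing data will be performed; missing data will not be replaced in this study, unless specified and for the following dates".

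SAP section 10 takes subgroup counts as percentages of the FAS.

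**The concern.** A level defined as the remainder absorbs missing information. An HR+ patient treated within a year of trastuzumab, but with an incomplete end date in the chart, has no interval under the SAP's day-based formula (12.1) and lands in No. So does a patient with no receptor result, or with one receptor negative and the other unrecorded. Such a patient is neither HR+ nor HR- under 8.4, yet still counts as off-label.

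The SAP's general promise to display missingness (8.3) does not help, because a variable with a remainder level is never missing. With percentages taken among the FAS, Yes and No add to 100% and leave no room for unknowns.

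At stake are the reported share of in-label use and the meaning of the No column. If chart completeness is unrelated to outcome, differences between the columns are diluted. If it is related, they can be distorted in either direction.

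**Working it through.** **Is the end date really left incomplete?** The Table 8 row is oddly labelled, since it attaches 'neoadjuvant' to post-surgery therapy. There are two readings.
- The row covers adjuvant therapy (supported by 12.3.1): the end date is not imputed.
- The row does not cover it: the date is unlisted, and the opening default of Appendix 1 gives no imputation.

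Both lead to the same place. Even if the general partial-date rule applied, "If the day and month are missing, the date will not be imputed", so some dates would stay open.

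**Reach.** Subgroup splits named per section: 11.1 has 8, 11.3 has 7, 12.1 has 9, 12.3.1 has 4, 12.4.1 has 3, 12.4.2 has 5, 13.1 has 2 and 13.2 has 5. The total is 43. EU label is one split in each of the eight sections, so 8/43 = 19% of splits.

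**Scale.** The plan's only quantitative design figure is the 95% half-width. At N = 120 (SAP 4.2), 1.96 × √(p(1−p)/120) gives 5.37, 7.16, 8.20, 8.77 and 8.95 points for p = 10% to 50%. The SAP states 5.4, 7.2, 8.2, 8.8 and 9, so it reproduces. The point does not depend on it, but it gives a yardstick.

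Let t be the true in-label share and m the share of patients who cannot be determined, taken as independent of label status. Neither is in the documents.
- Reported Yes = N·t·(1−m)
- No = N − Yes
- Understatement of the in-label share = t·m
- Truly in-label share of No = t·m / (1 − t + t·m)

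| t | m | Yes | No | Reported in-label | Understated by | Truly in label within No |
|---|---|---|---|---|---|---|
| 60% | 2% | 70.6 | 49.4 | 58.8% | 1.2 points | 3% |
| 75% | 5% | 85.5 | 34.5 | 71.2% | 3.8 points | 4.5/34.5 = 13% |
| 75% | 10% | 81.0 | 39.0 | 67.5% | 7.5 points | 9/39 = 23% |
| 90% | 10% | 97.2 | 22.8 | 81.0% | 9.0 points | 47% |
| 90% | 20% | 86.4 | 33.6 | 72.0% | 18.0 points | 64% |

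At t = 75% and N = 120 the half-width is 7.7 points, so m = 10% gives a bias about as large as the sampling error.

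**Dilution.** If a share w of No is truly in label and resembles the Yes group, the observed difference is (1−w) times the true one. With w = 13% to 23%, that is 87% to 77% of it.

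**Can month and year settle the question?** Often. Take trastuzumab ended March 2019 and neratinib started June 2019, with both days unknown. The shortest interval is 31 March to 1 June, 62 days; the longest is 1 March to 30 June, 121 days. Both are well inside one year. If a share r of incomplete dates is settled this way, m falls from q, the share incomplete, to q·(1−r).

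**Opposite direction.** A neratinib start with only the day missing is imputed to the first of the month. That shortens the interval by up to 30 days and can move a patient just beyond one year into Yes. It matters only close to the one-year limit.

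**The case against.** The strongest reply is that 8.4 states a substantive condition and does not require the day-based formula of 12.1. A programmer could classify the March/June patient as in label without imputing anything. That stands as a limit on size: the SAP neither provides nor forbids such logic, so a reader should not infer that every incomplete date is misfiled. It does not remove the defect, since unsettled cases still go to No and the practice is left to the programmer.

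The missing intervals should also be visible, because 12.1 tabulates the trastuzumab-to-neratinib interval by EU label and 8.3 promises missing counts. That would reveal the number in one table but would not separate those patients in any other. The table shells are not among the documents and might show a missing row.

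Unrecorded receptor status may be rare: SAP 11.3 lists ER and PR only as positive or negative, while Ki-67 and grade have an unavailable level. This stands; the incomplete end date is the main route.

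A reader might infer that most subgroup tables are affected. They are not. Splits by stage, pCR, risk, regimen or receptor status do not use this rule, and the whole-FAS description that answers the primary objective is untouched.

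A reader might also see a threshold conflict, because the SAP allows exactly one year while the protocol's background describes patients "who completed prior adjuvant trastuzumab-based therapy less than one year ago". That text describes the indication and is not an analysis rule. At most one boundary day is involved, so it is not part of this point.

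**Conclusion.** The point holds in a limited form. As written, the rule counts undeterminable patients as off-label in the EU-label tables of eight outcome sections. It understates in-label use and mixes unknown with off-label patients.

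The size cannot be read from the documents. With 75% truly in label and 5% to 10% undeterminable, the share is 3.8 to 7.5 points low and 13% to 23% of No is truly in label. Over the wider assumed ranges (t 60% to 90%, m 2% to 20%), the understatement runs from 1.2 to 18 points. These figures assume that gaps in the chart are unrelated to label status, and they ignore the small opposite effect of imputing neratinib start dates. Any use of month and year lowers them.

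Severity is moderate. It might be tempting to call this essential to repair, but the subgroup analyses are optional and descriptive, no primary outcome is tested, and log-rank comparisons are exploratory.

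**What to change.** In SAP 8.4, give EU label status three levels: Yes, No and Not determinable.

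- Assign No only on documented HR-negative status, a documented interval beyond one year, or documented absence of adjuvant trastuzumab-based therapy.
- Where the trastuzumab end date or the neratinib start date has month and year only, compute the shortest and longest possible intervals. Classify the patient when both fall on the same side of one year; otherwise use Not determinable. For this variable, the bounding replaces first-of-month imputation of the neratinib start.
- Report the Not determinable count in patient disposition (section 10).
- Clarify the label of the Table 8 row so that it is plain whether adjuvant therapy is covered.

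If gaps are unrelated to label status, the in-label share among classifiable patients then returns to its true value. It would rest on 120 × (1−m) patients: 114 at m = 5% and 108 at m = 10%.

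The cost is SAP wording and a few lines of derivation code, with no new data. The downside is a small third category and slightly smaller Yes and No groups.

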4.3.1 Primary outcome

Demographics and clinical profile of patients with early-stage HER2+ breast cancer will be described, for the full analysis set and by subgroup(s) of interest, if the number of patients allow, (see section 4.3.4). The following baseline data will be collected at study entry:

1. Patient demographic and clinical characteristics at neratinib initiation, unless stated otherwise:
 - Age (year of birth), gender, weight, height, body mass index (BMI)
 - Performance status using the Eastern Cooperative Oncology Group (ECOG), Karnofsky or any other scoring system at primary diagnosis of breast cancer and at neratinib initiation
 - Employment status
 - Date of primary diagnosis of breast cancer
 - Menopausal status at primary diagnosis of breast cancer
 - Location of the primary tumor at primary diagnosis of breast cancer
 - Histology of primary diagnosis of breast cancer
 - Histological grade (Grade 1, Grade 2, Grade 3)
 - Histological subtype (Ductal, Lobular, Other etc.)
 - Breast Cancer stage at the time of primary diagnosis, using the Tumor/Node/Metastasis (TNM) classification system (I, II, III)¹⁹
 - Pathological Stage (American Joint Committee on Cancer classification) at the time of primary diagnosis
 - Relevant comorbidities at neratinib initiation, including, but not limited to the following:
 - Renal disease
 - Liver disease
 - Gastro-intestinal disorders
 - Cardiovascular conditions
 - Skin and subcutaneous tissue disorders
 - Diabetes (Type I or II)
 - Tumor biology
 - HR status (estrogen receptor [ER] and progesterone receptor [PgR] status)
 - HER2 overexpression/amplification
 - Ki-67 (if available)
 - Grading

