4.3.4 Subgroups of interest

The following subgroups are of interest, based on patient characteristics at neratinib initiation (index date) or primary diagnosis of breast cancer. Analyses of primary, secondary, and exploratory outcomes may be performed for some or all of these subgroups, subject to pertinence and the number of patients in each subgroup.

1. Nodal status at initial diagnosis (0, 1-3, ≥ 4), Tumor size at initial diagnosis (T1, T2, \geq T3), Stage I vs Stage II+III
 - a. Low risk (Stage I and N- or pCR) vs high risk (Stage II/III or N+ or no pCR)
2. Previous adjuvant or neoadjuvant therapy (Yes/No)
3. Residual disease after neoadjuvant treatment (no pCR)
4. Prior trastuzumab-based regimen (trastuzumab only/ trastuzumab and pertuzumab/ T-DM1)

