11.3 Primary Breast Cancer Diagnosis

To describe the clinical profile of the patients, the below characteristics related to the primary breast cancer diagnosis will be presented for FAS and by subgroup EU label; Pathologic stage; Residual disease after neoadjuvant treatment; Risk profile; Previous adjuvant or neoadjuvant therapy and Prior trastuzumab-based regimen overall and last treatment (Section 8.4):

- Age at primary diagnosis of breast cancer, calculated as:
 - *Year of breast cancer diagnosis – Year of birth*
- Age at primary diagnosis of breast cancer category: < 40 years, 40 to 49 years, 50 to 59, 60 to 69, >=70
- HER2 overexpression/amplification testing:
 - Immunohistochemistry (IHC): Yes, No, Unknown
 - If IHC, the result obtained: IHC 3+ (positive), IHC 2+ (equivocal)
 - Fluorescence in situ hybridization (FISH): Yes, No, Unknown
 - If FISH, the result obtained: Positive, Equivocal
 - Chromogenic in situ hybridization (CISH): Yes, No, Unknown
 - If CISH, the result obtained: Amplified, Non-amplified
- HER2 overexpression/amplification testing combination of results: IHC and FISH, IHC and CISH

- Hormone receptor status: ER positive, PR positive, ER negative, and PR negative
 - If ER or PR positive: Receptor expression (%) score, Score unavailable
- Ki-67 protein levels category: Low, Medium, High, Unavailable
 - For each category: Ki-67 protein levels (%), Unavailable
- Primary tumor location: Left Breast, Right Breast
 - For each side the exact location: Upper-outer quadrant, Upper-inner quadrant, Lower-outer quadrant, Lower-inner quadrant, Nipple complex, Axillary tail, Other
- Sentinel lymph node biopsy performed: Yes, No, Unavailable
 - If yes: Positive, Negative
- Primary tumor histology: Infiltrating ductal carcinoma, Infiltrating lobular carcinoma, Invasive carcinoma, Tubular, Other
- Histological grade: G1 Well differentiated, G2 Moderately differentiated, G3 Poorly differentiated, G4 Undifferentiated, Unavailable
- Stage of Breast Cancer: TX, T0, T1, T2, T3, T4, Tis
 - If T1, specified category: T1a, T1b, T1c, Unavailable
 - If T2, specified category: T2a, T2b, Unavailable
- Regional Lymph Nodes (N): NX, N0, N1
- Number of lymph nodes involved: 0, 1-3, ≥ 4
- TNM stage: T0N1M0, T1N0M0...
- Pathologic stage (AJCC classification): I, IIA, IIB, IIIA, IIIB, IIIC

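### SAP 8.4 gives recorded pathologic stage priority even after neoadjuvant therapy, so some patients with Stage II/III at diagnosis can be filed as Stage I

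*SAP*

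**What the plan says.** SAP 8.4 forms the stage subgroup from one variable: "Pathologic stage (AJCC classification) at primary breast cancer: Stage I, Stage II+III". The fallback line is "If missing, derived as in 2", which I read as pointing to Table 2, the AJCC staging table in the same section. Neither line distinguishes patients by treatment sequence.

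The stage row of the primary outcome in SAP 11.3 is "Pathologic stage (AJCC classification): I, IIA, IIB, IIIA, IIIB, IIIC". The same list has separate T and N rows, the number of nodes involved, and a combined row beginning "TNM stage: T0N1M0, T1N0M0". None of these is labelled clinical, pathologic or post-treatment.

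Protocol 4.3.1 lists two stage items, both dated to diagnosis. One is "Breast Cancer stage at the time of primary diagnosis, using the Tumor/Node/Metastasis (TNM) classification system (I, II, III"); the other is "Pathological Stage (American Joint Committee on Cancer classification) at the time of primary diagnosis".

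Neoadjuvant patients are part of the population and have their own subgroup in SAP 8.4: "Neoadjuvant + Post neoadjuvant, defined as, at least one neoadjuvant and one adjuvant treatment". SAP 12.3.1 places neoadjuvant therapy before surgery.

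**The concern.** A pathologic stage is read from the surgical specimen. This is general staging knowledge, not something the documents state. Given the sequence in SAP 12.3.1, the specimen of a neoadjuvant patient comes after systemic treatment, so its stage can reflect response as well as initial extent. A patient with Stage III at diagnosis and a small node-negative residual tumour could be recorded as Stage I. The fallback would not correct this, because the field is not missing. For patients who had surgery first, the same field describes disease before adjuvant therapy. One variable could then hold two different quantities.

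At stake is a row of the primary outcome, together with the stage columns of the tables in SAP 11.1, 11.3, 12.1 and 12.3.1. If post-treatment stage was entered, the cohort would look earlier-stage than it was at diagnosis. SAP 12.3.1 would be tabulating neoadjuvant therapy by a variable that the therapy had changed. SAP 11.3 would be tabulating stage by pCR status, although response partly determines that stage.

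**Working it through.** **The plan's own precision figure.** SAP 4.2 gives 95% half-widths at n = 120 of 5.4, 7.2, 8.2, 8.8 and 9% for proportions of 10 to 50%. The formula 1.96 × √(p(1 − p)/120) gives 5.37, 7.16, 8.20, 8.77 and 8.95%. The figures are reproduced, and 8.2 points (p = 30%) serves as the yardstick below.

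**Size of a possible misfiling.** The documents give no neoadjuvant share, stage mix or downstaging rate, so all of these are assumed:

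- n = 120 (SAP 4.2)
- Stage I at diagnosis: 30%, i.e. 36 patients (assumed)
- f, share with neoadjuvant therapy: 20-60% (assumed)
- s, Stage II/III at diagnosis among those: 70-90% (assumed)
- d, share of those recorded as Stage I after treatment: 0-50% (assumed; 0 is the case where sites entered pre-treatment stage)

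Shift in the Stage I share = f × s × d. Patients moved = 120 × f × s × d. Misfiled share of the Stage I group = shift / (0.30 + shift).

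| f | s | d | Patients moved | Shift (points) | Misfiled share of Stage I |
|---|---|---|---|---|---|
| any | any | 0 | 0 | 0 | 0% |
| 20% | 70% | 10% | 1.7 | 1.4 | 4% |
| 40% | 70% | 30% | 10.1 | 8.4 | 22% |
| 40% | 90% | 30% | 13.0 | 10.8 | 26% |
| 60% | 90% | 50% | 32.4 | 27.0 | 47% |

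For the third row, 0.40 × 0.70 × 0.30 = 0.084; 120 × 0.084 = 10.1; 0.084 / 0.384 = 22%. That shift is about as large as the stated half-width of 8.2 points. It would be a bias, so the confidence interval would not reflect it.

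**Can Table 2 take more patients?** Not as it stands. T0N1M0 appears under both IB and IIA, and so does T1N1M0. These two combinations straddle the Stage I / Stage II+III boundary and cannot be placed on either side. T0N0M0 has no row, and the stage row in SAP 11.3 starts at I. A complete responder with a post-treatment entry would therefore more likely have no stage than be called Stage I.

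**Reach.** Stage is a listed subgroup in SAP 11.1, 11.3, 12.1 and 12.3.1. It is not listed in 12.4.1 or 12.4.2 (adverse events, diarrhea) or in 13.2 (time to event).

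**The case against.** The strongest objection is that the labels point to diagnosis: both stage items in Protocol 4.3.1 are dated there, and the SAP row sits under the primary diagnosis heading. A site may have entered the pre-treatment stage, or left the field blank, which triggers the fallback. This stands. A reader might infer that downstaged patients are in fact counted as Stage I, but no text says that post-treatment stage is entered, and the eCRF instructions are not in the documents. The priority rule remains open to the problem, because for these patients the word pathologic and the timing at diagnosis pull in different directions.

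Second, SAP 11.3 already shows T, N and TNM rows and splits its rows by treatment sequence and by pCR. This makes any mixing partly visible there. It does not separate the stage-subgroup columns in the other tables.

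Third, a reader might infer that SAP 7.10 leaves out a change from the protocol. Protocol 4.3.4 reads "Nodal status at initial diagnosis (0, 1-3, ≥ 4), Tumor size at initial diagnosis (T1, T2, \geq T3), Stage I vs Stage II+III": the timing phrase belongs to nodal status and tumor size, and the kind of stage is left open. Pathological stage was already a protocol item. Choosing it fills a gap and is not clearly an undeclared change.

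Fourth, a reader might infer that the Risk subgroup is distorted to the same degree. A downstaged patient with residual tumour is High risk through the no-pCR criterion whatever the recorded stage. A wrong Stage I would only add a Low criterion, and the overlap of the two definitions is a separate matter.

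Finally, the subgroup tables are optional and primary outcomes are not tested. This limits the consequences to description, but description is the study's primary objective.

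**Conclusion.** The point holds as a weakness in the derivation rule, not as a demonstrated misclassification. SAP 8.4 prefers the stage measure that treatment can alter, including in patients treated before surgery, and uses T/N/M only as a fallback. Some patients with Stage II/III at diagnosis can therefore be filed as Stage I.

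The frequency is unknown and may be zero. Under the stated assumptions, 0 to 32 of 120 patients move, the Stage I share rises by 0 to 27 points, and 0 to 47% of the Stage I group is misfiled. The conclusion rests on the premise that a pathologic stage comes from the surgical specimen, and on at least some sites having entered it after treatment. The effect is confined to descriptive tables. The change is worth making because a better-anchored derivation appears to be available from fields already tabulated.

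**What to change.** 1. Check the eCRF completion instructions for what sites were asked to enter, and whether the T and N fields are pre-treatment.
2. If they are, reverse the precedence in SAP 8.4 and 11.3 for patients with at least one neoadjuvant therapy: derive stage from T and N at primary diagnosis. Use recorded pathologic stage first only for patients who had surgery first.
3. If the timing of T and N cannot be confirmed, present stage by treatment sequence with a footnote on the staging basis.
4. Resolve the duplicate Table 2 rows for T0N1M0 and T1N1M0. Otherwise the new rule sends more patients into combinations that cannot be classified.
5. If recorded pathologic stage proves to be post-treatment, show it as a separate row and keep it out of the Stage and Risk subgroups.

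The cost is SAP wording, one derivation, the Table 2 correction and the eCRF check. Protocol 4.7.1 allows a SAP amendment before database lock; after lock, the change would be reported as a deviation. The downside is that the staging source then differs by treatment sequence, which needs a footnote, and that some patients become stage unknown.

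### SAP Table 2 gives two stages for T0N1M0 and T1N1M0, and section 8.4 counts NX as node-negative, so some patients get an undetermined stage group or an unsupported N- label

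*SAP*

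**What the plan says.** SAP section 8.4 defines the stage subgroup as "Pathologic stage (AJCC classification) at primary breast cancer: Stage I, Stage II+III". If the recorded stage is absent, the rule is "If missing, derived as in 2". The table that follows in that section, Table 2, maps T, N and M to an AJCC stage. It has two rows for T0N1M0 (IB and IIA) and two for T1N1M0 (IB and IIA), with no rule for choosing between them. A note below it says "N2 and N3 are not collected in the CRF, this regional lymph node categories will be identified by" the count category of four or more involved nodes.

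The same section gives the risk subgroup as "Risk: Low risk (Stage I or N- or pCR), High risk (Stage II/III or N+ or no pCR"). Node-negative is set by "N-, defined as, the electronic case report form (eCRF) nodal status category of NX or N0", and node-positive means one or more nodes. Protocol section 4.3.4 has a different Low-risk rule: "Low risk (Stage I and N- or pCR) vs high risk (Stage II/III or N+ or no pCR").

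SAP section 11.3 lists the nodal data to be tabulated: "Regional Lymph Nodes (N): NX, N0, N1", and the number of involved nodes as 0, 1-3 or ≥4. SAP section 8.3 says that missing data will, in general, not be imputed.

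**The concern.** Two inputs to the subgroup derivations do not do what a pre-specified rule should.

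First, IB belongs to Stage I and IIA to Stage II+III. A patient with missing recorded stage and T0N1M0 or T1N1M0 therefore has two derived groups, and the one that reaches the tables depends on the program rather than the plan.

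Second, NX is a category separate from N0, yet it earns the label N-. The SAP treats NX as too little to derive a stage at M0 but enough to call a patient node-negative. That fits badly with the general rule against imputation. With nodal status dropped as a subgroup of its own (SAP section 7.10), N- and N+ act only inside the risk classes, where the pooling cannot be seen.

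The primary objective is to describe the clinical profile of these patients. Stage and risk are among the factors by which that profile, the treatment patterns and the treatment history are to be broken down.

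**Working it through.** **Step 1: the lookup.** Apart from the two rows for any T, Table 2 has 17 rows, all at M0. They cover 15 distinct T-N combinations, so two combinations are duplicated. Crossing each T category with each nodal category that is collected gives:

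| Combination at M0 | Stage(s) returned | Effect on Stage I vs II+III |
|---|---|---|
| T0 N1 | IB, IIA | undetermined |
| T1 N1 | IB, IIA | undetermined |
| T0 to T3, ≥4 nodes | IIIA, IIIC | none, both in II+III |
| T4, ≥4 nodes | IIIB, IIIC | none, both in II+III |
| any T with NX | no row | cannot be derived |
| TX with N0 or N1; T0 N0; Tis N1 | no row | cannot be derived |

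Only T0N1M0 and T1N1M0 straddle the analysed cut.

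**Step 2: can collected data separate the two rows?** Section 11.3 lists one N1 category, node counts in three bands, and sentinel biopsy as positive or negative. None of these divides N1 into a part that maps to IB and a part that maps to IIA.

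**Step 3: what NX does to risk class.** Take an NX patient with stage missing, no pCR result (for example, no neoadjuvant therapy) and no recorded positive node count. Stage cannot be derived at M0 and no High-risk criterion is met. N- is met through NX, so the patient is Low risk on NX alone. If the same patient has a recorded count of one or more nodes, both N- and N+ are met.

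**Step 4: the risk rule around it.** Stage (I, II/III) by node (N-, N+) by pCR (yes, no, not applicable) gives 2 × 2 × 3 = 12 profiles. Under the SAP wording, 8 of 12 meet both Low and High. Under the protocol wording, read as (Stage I and N-) or pCR, 4 of 12 do. SAP section 7.10 does not list this change.

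**Step 5: scale.** The planned number is 120 (SAP section 4.2). The rates below are assumptions, since the documents give none.

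- Undetermined stage group = 120 × share with stage missing × share T0/T1 N1 among them. With 10-40% and 10-20%: 120 × 0.10 × 0.10 = 1.2 to 120 × 0.40 × 0.20 = 9.6. With 5-30% and 10-30%: 0.6 to 10.8.
- NX pooled with N0, at 2-10%: 120 × 0.02 = 2.4 to 120 × 0.10 = 12.
- NX with stage also missing, treated as independent: 120 × 0.02 × 0.10 = 0.24 to 120 × 0.10 × 0.40 = 4.8, before removing patients with a pCR result.

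**The case against.** The strongest reply is that Table 2 is only a fallback. A recorded stage is never overridden, the subgroup analyses are optional, no testing is planned for primary outcomes, and neither stage nor risk is among the time-to-event subgroups of SAP section 13.2. NX, N0, N1 and node counts are also tabulated in section 11.3, so a reader can see how many patients are NX. All of this stands, and it limits the reach of the point.

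The paired rows may also be the trace of an N1 sub-category mark lost when the PDF was read. That is possible, but it would not rescue the derivation, because section 11.3 lists no such sub-category. The eCRF itself is not available to settle the matter.

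Four stronger readings are tempting, and the documents do not support them:

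- **That these patients are wrongly classified.** For T0N1M0 and T1N1M0 the derived group is undetermined. For NX the true nodal status is unknown, so N- is unsupported rather than shown to be false.
- **That Stage I is inflated.** A program that keeps the last row read returns IIA, and one that keeps the first returns IB. The direction is open.
- **That every NX patient's risk class turns on NX.** If High takes precedence over Low under the SAP wording, an NX patient with Stage II/III or no pCR is High, and one with recorded Stage I or with pCR who meets no High criterion is Low anyway. NX decides only when stage is missing and there is no pCR result.
- **That a large part of the Stage I or Low-risk group is affected.** Dividing by an assumed group of 30 to 40 gives 9.6/40 = 24% to 12/30 = 40% at the upper ends, but 1.2/40 = 3% and 2.4/40 = 6% at the lower ends. The group size is itself a guess, and the division assumes that every affected patient lands in that group.

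**Conclusion.** The point holds in a limited form. The derived stage group is undetermined for T0N1M0 and T1N1M0 patients whose recorded stage is missing, and the N- label is unsupported for NX patients. Both follow from stated rules, not from missing detail.

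The reach is descriptive: the subgroup tables of SAP sections 11.1, 11.3, 12.1 and 12.3.1, and the subgroup counts in section 10. The size is unknown. On the assumed rates it is about 1 to 10 patients for stage and 2 to 12 NX patients out of 120. Between about 0.2 and 4.8 of the NX patients would have their risk class set by NX alone if High takes precedence. Under the protocol's Low-risk rule NX matters in one further case: it supplies the N- half of the condition for a patient with recorded Stage I and no pCR result.

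The overlap between the Low and High classes is the wider defect in the same lines. Fixing it would not by itself correct the NX input.

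**What to change.** - **Stage.** When the recorded stage is missing and the combination is T0N1M0 or T1N1M0, set the derived stage group to unknown, unless the sponsor states one class and its basis. Show a sensitivity count with these patients in each group. Simply deleting the IB rows is not justified by the SAP: in the High-risk definition N+ and Stage II/III are alternatives joined by OR, which does not show that N1 implies Stage II.
- **Nodal status.** Define N- as N0 only. For NX, use the recorded number of involved nodes if there is one. Otherwise code nodal status as unknown, so that it does not contribute to Low risk.
- **Risk.** Make these edits together with a mutually exclusive Low/High rule that has an unknown category and is reconciled with protocol section 4.3.4. Record the change in SAP section 7.10.

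The cost is a short SAP amendment, which protocol section 4.7.1 allows before database lock, and a few more patients in an unknown category. No new data are needed.
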